#### **3.4.2. Procedures after stopping study.**

Once stopped, the study team will review the outcomes of the patients infused and report to regulatory authorities for review. The study will not resume until approvals to continue are granted by the study team and regulatory authorities including the IRB, DSMB and FDA.

#### **3.4.3. Off Study Criteria**

**3.4.3.1.** Completion of study specified procedures.

**3.4.3.2.** Refusal of further study follow-up by patient or legal guardian.

**3.4.3.3.** Lost to follow up.

**3.4.3.4.** Death

## 4. STATISTICAL CONSIDERATIONS

### 4.1. Study Design Synopsis

This study is a dose-finding safety study followed by a randomized, controlled pilot study to evaluate the safety and clinical effects of administering banked partially HLA matched SARS-CoVSTs to hospitalized COVID19 patients.

### 4.2 Dose Finding Phase

Three dose levels will be evaluated (Section 2.5). Dose escalation will be guided by the standard 3+3 design in order to determine the maximum tolerated dose (MTD) of SARS-CoVSTs. Detailed definitions of DLT are described in Section 3.1 and Section 3.4.1. The specific procedure is as follows: Starting from dose level 1 and escalating to the highest level sequentially, a cohort of three patients will be enrolled at each dose level, with a stagger to wait until the first patient on each dose level completes the 14-day toxicity monitoring window prior to enrollment of the other two patients. Dose level to the subsequent new cohort will not be assigned until the patients in the previous cohort have finished their 14-day period and their toxicity evaluations have become available. If no DLT is observed in any of the first 3 patients, the dose level will be escalated to the next dose level. If DLT is observed in 1 of the 3 patients, 3 more patients will be enrolled at the same dose level. If DLT is observed in no more than 1 out of 6 patients then we will advance to the next dose level. If DLT is observed in 2 or more patients at a same dose level then the MTD has been exceeded and the next lower dose level will be considered as the MTD level, if 6 patients have already been treated at that level. If only 3 patients have been studied at the MTD, 3 more patients will be enrolled at the MTD level to confirm that no more than 1 out of 6 patients have a DLT. Escalation will not proceed past dose level 3. If none of the dose levels has more than one patient who develops a DLT, then the highest dose level will be defined as the MTD. Patients who develop DLTs or complete 14-day monitoring periods after the VST infusion are considered DLT evaluable. Any patients who drops off the study early before day 14 due to a non-DLT-related reason will be replaced.

### 4.3 Randomized Pilot Trial Phase

After the MTD is determined, the study will continue to the randomized pilot trial phase. Consented and eligible patients in this phase will be randomized in a 1:1 ratio to receive either SARS-CoVSTs on the MTD level or standard of care. Randomization will employ the permuted blocks method with a block size of 4 (2 in the treatment arm and 2 in the control arm). No stratification will be used in randomization.

In the randomized pilot trial phase, we will continuously monitor the safety of SARS-CoVST infusions in the treatment arm so that the accrual can be halted early if there is an unexpectedly high rate of treatment-related adverse events. Treatment-related adverse events (tAE) are defined in Section 3.1. Every patient who is randomized to the treatment arm and infused with SARS-CoVSTs will be evaluated for tAE and all patients who have tAEs will be followed until toxicities resolve. A tAE rate of greater than or equal to 25% is considered excessive. The occurrence of tAEs will be monitored using a stopping guideline based on a Pocock-type boundary method [24]. The following sequential stopping boundaries will be used:

Number of Patients	1-2	3	4-5	6-7	8-9	10-12	13-15	16-17	18-20
Number of tAEs <	-	3	4	5	6	7	8	9	10

The accrual will be halted if the number of tAEs is equal to or exceeds the boundary in the above table. Under this sequential stopping rule, the probability of early stopping is 5% if the true tAE rate is 25%, and the probability of early stopping will be high at 67.5% if the true tAE rate is 50%.

#### **4.4 Stopping Rules**

Per [Section 3.4.1](#), halting rules for the study have been defined and these align with DLTs. The study will not resume until approval to continue are granted by the study team and regulatory authorities including the IRB, DSMB and FDA.

#### **4.5. Sample Size Determination and Design Characteristics**

A maximum of 18 DLT evaluable patients will be accrued to the dose finding phase of the study. Based on our previous studies and experiences, we do not anticipate seeing any VST-related AE at any dose level and we expect to enroll 12 for the phase.

In the randomized pilot trial phase, a total of 40 patients will be enrolled and randomized (20 in the treatment arm and 20 in the standard of care arm). The safety endpoint in this phase is tAE. The study is designed to monitor toxicity due to SARS-CoVSTs closely so the trial can halt accrual early if its toxicity rate is excessive. For this purpose, a tAE rate of 25% is considered excessive, while a rate below 25% is considered acceptable. Based on our current experience with VST therapy, we anticipate the actual tAE rate to be much lower around 5%. With 20 patients in the treatment arm, if the observed tAE rate is 5%, the corresponding 95% confidence interval will be 0.1%-24.9% which excludes 25%, and the chance of observing more than 3 tAEs in the treatment arm is only about 1.6%. The efficacy endpoint in this phase is clinical response, defined as improvement in at least 2 points in the WHO Ordinal Scale or discharge from hospital by day 7 post randomization. Patients' outcome will be dichotomized as 'having a response' or 'not having a response'. Patients who died before day 7 will be deemed as 'not having a response'. Based on current publications of novel COVID-19, we expect 90% patients in the treatment arm and 50% patients in the control arm will have a response by day 7. A sample size of 40 will provide 83% power to detect the 40% increase in response rate for the SARS-CoVSTs treatment compared to the standard of care treatment, with a Fisher's exact test at a 5% one-sided significance level.

We anticipate about one third subjects who are considered for study participation will not meet all inclusion criteria, thus we will consent 87 subjects to have 58 eligible patients (18 in dose finding phase and 40 in the randomized pilot trial phase).

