#### **4.6. Data Analysis**

All patients who received VSTs infusions or standard of care will be included in the safety analyses. All patients infused with SARS-CoVSTs and finish their 14-day toxicity observation or develop a DLT/tAE before day 14 are considered DLT/tAE evaluable. All efficacy analysis will be based on the intent to treat (ITT) population, defined as eligible and randomized subjects.

Adverse events and corresponding toxicity grades after study treatment will be summarized descriptively by phases then arms. Toxicity information including the type, severity, time of onset, time of resolution, and the probable association with study treatments will be tabulated and summarized. Incidence of DLT/tAE in patients who receive VST infusions defined in [Section 3.1 and 3.4.1](#), will be reported with rates and 95% binomial exact confidence intervals.

Clinical responses will be summarized using rates and 95% binomial exact confidence intervals for the randomized pilot trial phase by arms and compared using Fisher's exact test. Anti-COVID19 efficacy assessed by the WHO ordinal scale will be evaluated every day up to day 14 post-randomization. The assessments will be summarized using descriptive statistics such as medians and ranges. Plots of the assessments over time will be generated for each patient to graphically illustrate the pattern and trend of clinical status. The changes in scales by day 14 post randomization will also be computed; percentages of patients with stable ordinal scale, with worse or improved scales will be summarized by arms.

Clinical exploratory end points (requirement of supplemental oxygen, progression to mechanical or advanced ventilation or ICU, mortality rate, duration on oxygen supplementation, duration of ventilation free, duration of organ failure-free, durations of ICU stay and hospital stay, time to RT-PCR virus negativity) will be summarized in a descriptive nature by arms. Categorical variables will be summarized by frequencies and percentages, and continuous variables will be summarized by means, standard deviations, medians, interquartile ranges. Clinical endpoints will be compared between arms using Fisher's exact tests or Wilcoxon rank sum tests, whichever is appropriate. All statistical tests for clinical exploratory endpoints will be considered exploratory

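### The one-sided 5% Fisher test for the primary response comparison uses at most 2.7% of its 5% level at 20 per arm; a one-sided 5% Boschloo test would add 5 to 9 points of power with the same patients

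*Protocol*

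**What the plan says.** Protocol section 4.5 sets out the primary efficacy comparison of the randomized phase in full.

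- Assumed rates: "we expect 90% patients in the treatment arm and 50% patients in the control arm will have a response by day 7".
- Allocation: "20 in the treatment arm and 20 in the standard of care arm".
- Test, level and side: "with a Fisher's exact test at a 5% one-sided significance level".
- Resulting power: "A sample size of 40 will provide 83% power to detect the 40% increase in response rate".

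Protocol section 4.6 names the same test for the same endpoint. Responses are to be given as rates with exact 95% intervals "by arms and compared using Fisher's exact test". It repeats neither the level nor the side. On the analysis set it says: "All efficacy analysis will be based on the intent to treat (ITT) population, defined as eligible and randomized subjects".

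**The concern.** Fisher's test conditions on the total number of responders. With 20 per arm, few outcomes are possible for each total, so the attainable p-values are widely spaced and the true type I error falls well short of the nominal level. The sponsor has accepted a one-sided 5% risk of a false positive, yet the chosen test cannot use much more than half of it.

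The cost is power. In a 40-patient comparison, one responder more or fewer can decide the result, and the 40-point difference in section 4.5 is large. If the real effect is smaller, power falls quickly and the conservatism of the test costs more. An exact test that still respects the 5% limit would recover part of this loss without changing the trial.

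**Working it through.** **Inputs (Protocol section 4.5).** 20 per arm; response 90% with treatment and 50% with control; Fisher's exact test, one-sided 5%. All 40 randomized patients are taken to have a response status.

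**Formulas.** Let a and b be the responders among 20 treated and 20 control patients, which gives 21 × 21 = 441 outcomes.

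- One-sided Fisher p-value: p(a,b) = Σ over k ≥ a of C(20,k)·C(20,a+b−k) / C(40,a+b).
- Fisher rejects when p(a,b) ≤ 0.05.
- Power = Σ over rejected (a,b) of Bin(a; 20, πT)·Bin(b; 20, πC).
- True size = the same sum with πT = πC = π, maximised over π.
- Boschloo's test orders outcomes by the Fisher p-value, but takes the largest cut-off whose maximum true size is still at most 5%.

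**Step 1: the plan's own figure.** With πT = 0.90 and πC = 0.50, the one-sided 5% Fisher test has power 0.8375. The stated 83% is reproduced. It is an exact figure and already includes the test's conservatism; a normal approximation would have given 89.2%.

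**Step 2: true size of the Fisher test.** The maximum over π is 0.0266, reached at a common rate of about 0.68. The size is 0.021 at a common rate of 0.50 and 0.008 at 0.90. At its worst the test spends 2.66 / 5 = 53% of the permitted error.

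**Step 3: Boschloo at the same level.** The cut-off on the Fisher p-value is 0.0776, with maximum true size 0.0428. Admitting the next attainable p-value (0.0880) would take the maximum size to 0.0511, above the limit. Fisher rejects in 119 outcomes and Boschloo in 130. The 130 include all 119, so there are 11 more.

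**Step 4: power of both tests, one-sided 5%.**

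| Treatment vs control | Fisher | Boschloo | Gain (points) |
|---|---|---|---|
| 90% vs 50% | 83.7% | 88.8% | 5.1 |
| 80% vs 50% | 53.1% | 61.2% | 8.1 |
| 90% vs 60% | 61.9% | 70.7% | 8.8 |

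**Step 5: check of the gain by hand.** At 90% vs 50%, most of the 5.1 points come from two of the added outcomes:

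- 17 vs 12 responders (Fisher p = 0.0776): 0.1901 × 0.1201 = 0.0228.
- 18 vs 13 responders (Fisher p = 0.0637): 0.2852 × 0.0739 = 0.0211.

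Together they give 0.0439 of the 0.0508 gained. Another added outcome is 15 vs 9 responders, a 30-point difference: Fisher p = 0.053 does not reject, and Boschloo does.

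**Step 6: other tests at the one-sided 5% level.** An unconditional test ordered by the pooled z statistic has power 86.6% (maximum size 4.31%), a gain of 2.8 points at 90% vs 50%. The mid-p version of Fisher has the same power and maximum size here as Boschloo.

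**The case against.** The strongest defence is that nothing in section 4.5 is wrong. The power is right for the test named, it exceeds 80% at the design alternative, and Fisher's test is a conventional exact choice for two arms of 20. Conservatism errs on the safe side, and the protocol nowhere says the sponsor wants to use the full 5%. The size of the gain also depends on the comparator: 5.1 points with Boschloo but 2.8 with the pooled-z test. The larger gains are for effects the pilot was not sized to detect, and even there Boschloo reaches only 61% and 71%.

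All of this stands as a limit on the weight of the point. It does not remove it. The protocol itself fixes Fisher's test, and Boschloo at the same one-sided 5% level rejects whenever Fisher does while keeping the maximum type I error below 5%. Within the sponsor's own error limit, nothing is given up in return for the power.

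A reader might also infer that section 4.6 abandons the one-sided test, so that the stated 83% is really about 74%. A two-sided 5% Fisher test does have power 74.2% at 90% vs 50%, but the protocol does not call for one. Section 4.5 fixes one-sided 5% for this endpoint, and section 4.6 names the same test and is merely silent on the side. Its 95% intervals describe the response rate in each arm separately; they are not intervals for the treatment difference and imply nothing about the side of the test. Repeating level and side may also be left to a statistical analysis plan, which is not shown.

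**Conclusion.** The point holds as a free improvement in the choice of test. The stated 83% is correct for the one-sided 5% Fisher test, but that test's true size never exceeds 2.7% against the 5% allowed. A one-sided 5% Boschloo test keeps type I error at or below 4.3% and adds 5.1 points of power at the design alternative, and 8 to 9 points at 80% vs 50% and 90% vs 60%.

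These figures assume exactly 20 per arm, a response status for every randomized patient, independent outcomes, and a one-sided 5% level as in section 4.5. The two alternatives with smaller effects are illustrative and are not taken from the protocol. The documents do not support calling the power figure wrong or the two sections contradictory.

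**What to change.** Before analysis, and before response data are looked at by arm, name a one-sided 5% Boschloo exact test for the primary response comparison in section 4.6, and restate the power in section 4.5 as about 89% for 20 per arm at 90% vs 50%. The per-arm rates and exact 95% intervals can stay as they are.

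If the sponsor keeps Fisher's test, the 83% needs no change. Adding the one-sided 5% level to section 4.6 would then be a helpful clarification for anyone working from that section alone.

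The cost is about one sentence in each section. Boschloo's test is available in standard software, and no patients, visits or data are added.

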#### **4.6. Data Analysis**

All patients who received VSTs infusions or standard of care will be included in the safety analyses. All patients infused with SARS-CoVSTs and finish their 14-day toxicity observation or develop a DLT/tAE before day 14 are considered DLT/tAE evaluable. All efficacy analysis will be based on the intent to treat (ITT) population, defined as eligible and randomized subjects.

Adverse events and corresponding toxicity grades after study treatment will be summarized descriptively by phases then arms. Toxicity information including the type, severity, time of onset, time of resolution, and the probable association with study treatments will be tabulated and summarized. Incidence of DLT/tAE in patients who receive VST infusions defined in [Section 3.1 and 3.4.1](#), will be reported with rates and 95% binomial exact confidence intervals.

Clinical responses will be summarized using rates and 95% binomial exact confidence intervals for the randomized pilot trial phase by arms and compared using Fisher's exact test. Anti-COVID19 efficacy assessed by the WHO ordinal scale will be evaluated every day up to day 14 post-randomization. The assessments will be summarized using descriptive statistics such as medians and ranges. Plots of the assessments over time will be generated for each patient to graphically illustrate the pattern and trend of clinical status. The changes in scales by day 14 post randomization will also be computed; percentages of patients with stable ordinal scale, with worse or improved scales will be summarized by arms.

Clinical exploratory end points (requirement of supplemental oxygen, progression to mechanical or advanced ventilation or ICU, mortality rate, duration on oxygen supplementation, duration of ventilation free, duration of organ failure-free, durations of ICU stay and hospital stay, time to RT-PCR virus negativity) will be summarized in a descriptive nature by arms. Categorical variables will be summarized by frequencies and percentages, and continuous variables will be summarized by means, standard deviations, medians, interquartile ranges. Clinical endpoints will be compared between arms using Fisher's exact tests or Wilcoxon rank sum tests, whichever is appropriate. All statistical tests for clinical exploratory endpoints will be considered exploratory

Time to clinical failure is defined as the days from VST infusion to date of death, mechanical ventilation, ICU admission, or study withdrawal, whichever occurs first. Patients without those clinical failure events up to 14 days will be considered censored. Time to clinical failure will be estimated in each arm by the Kaplan-Meier method and compared using log-rank tests.

Laboratory data, which include expansion and persistence of infused VSTs, inflammatory markers, biomarkers of T cell activation, will be summarized with appropriate summary statistics. Changes from pre- to post-infusion will be plotted for each patient who receives the VST infusion over time and assessed using paired comparisons when appropriate.

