**2.6. Inclusion and Exclusion Criteria.**

The same inclusion/exclusion criteria will apply to both phases of the study.

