**2.6.1. Inclusion Criteria.**

1. SARS-CoV-2 infection confirmed by PCR from a nasopharyngeal swab or other accepted specimen type. (If testing was performed $\geq 5$ days before enrollment, this must be repeated and accept only if positive again). Date of COVID test must be $\leq 5$ days prior to infusion
2. Currently hospitalized adult patient ( $\geq 18$ years of age) requiring medical care for COVID19
3. Peripheral oxygen saturation (SpO2) $\geq 92\%$ on room air
4. Hgb $\geq 7.0$ gm/dl
5. Negative pregnancy test (if applicable)
6. Patient or parent/guardian capable of providing informed consent (may be obtained electronically)
7. Evidence of pulmonary infiltrates on chest imaging. Any chest imaging findings which would be consistent with COVID19 would qualify (Eg: ground glass opacities, multifocal infiltrates etc.)

8.	High risk of requiring mechanical ventilation as defined by at least two of the following :
a.	Age $\geq$ 60 years of age
b.	Age $\geq$ 75 years of age (counts as meeting two criteria)
c.	Hypertension
d.	Chronic cardiovascular disease other than HTN (eg: Coronary artery disease, congestive heart failure or cardiomyopathies).
e.	Diabetes Mellitus
f.	Obesity (BMI $\geq$ 30)
g.	Obesity (BMI $\geq$ 40, counts as meeting two criteria)
h.	Active cancer diagnosis or ongoing (within 3 months) cytotoxic chemo/ radio-therapy for a cancer
i.	Post-hematopoietic stem cell or solid organ transplantation status
j.	Immunodeficiency states including HIV infection on antiretroviral therapy (except those listed as exclusion criteria #1, #7 and #10) as determined by the treating physician (eg: receiving immunosuppressive therapy like rituximab or congenital immunodeficiency syndromes, prior treatment with chemotherapy > 3 months ago but per investigators discretion could have lingering effects on the immune system, eg: chemotherapy regimens for lymphomas, ALL or AML etc.)
k.	Chronic obstructive pulmonary disease (COPD)
l.	Current everyday smoker
m.	Chronic kidney disease (eGFR < 30 mL/min/1.73 m  )
n.	Bronchial asthma (on active treatment prior to admission, eg. Use of rescue inhalers or inhaled corticosteroids or other treatments to prevent/treat attacks).

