**2.6.2. Exclusion Criteria.**

1.	Received ATG, Campath or other T cell immunosuppressive monoclonal antibodies in the 28 days prior to screening for enrollment
2.	Requiring mechanical ventilation at time of T cell infusion
3.	Alanine aminotransferase or aspartate aminotransferase > 5 x upper limit of normal
4.	If previously undergone an allogeneic HSCT and have evidence of active acute GVHD $\geq$ grade 2
5.	Uncontrolled relapse of malignancy
6.	Requiring vasopressors
7.	Known history of autoimmune disease except prior thyroiditis
8.	Is not suitable at the discretion of the treating physician
9.	Patients on > 6 mg/day of dexamethasone (IV) per day or equivalent
10.	> grade 1 CRS per ASTCT criteria
11.	Patients should not be enrolled on any other interventional clinical trials for COVID19. Patients may receive routine care for COVID19 per institutional standards (including antivirals such as remdesivir or other FDA-EUA approved products and thromboprophylaxis).

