### **2.6.3. Informed Consent and Randomization.**

The informed consent process will begin at recognition of a subject who meets all eligibility criteria and consents to participation after a discussion with the study team (informed consent process). Consent may be obtained by teleconference. Once enrolled, blood will be taken from the subject for baseline immune response assessment and HLA-typing and if a partially HLA-matched VST line is available the subject will either receive treatment (dose escalation phase) or will be randomized (Randomized trial phase) to receive the partially matched VST line (in the treatment arm) or standard of care (in the control arm). If no VST line is identified, the patient will not proceed to treatment or randomization and will be removed from the study, but statistics on the proportion of patients who sign consent but are not treated or randomized will be reported.

Applicable only to the randomized phase, once randomized to the treatment arm, the patient must be infused with VSTs within 48 hours of randomization.

All consented patients will be registered in the online collaborative research environment (Forte's OnCore® eResearch CTMS), a Clinical Research Management System available at BCM Dan L. Duncan Comprehensive Cancer Center.

Enrollment to the dose escalation phase will be staggered. The first patient enrolled on each of the 3 dose levels (DL1, DL2 and DL3) will have to complete the 14-day toxicity monitoring window prior to enrollment of the next patients. Prior to dose escalation, all patients at a particular dose level should have completed the minimum 14-day toxicity monitoring window before enrolling to a higher dose level.

After the dose finding phase, patients will be randomized in a 1:1 ratio to receive SARS-CoVSTs at the MTD level or standard of care. Randomization will be performed in OnCore and use the permuted block method with a block size of 4 (2 in the treatment arm and 2 in the control arm). The purpose for a permuted block method is to ensure fairly random assignment during specific periods of surge with COVID19.

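### The efficacy set is called ITT but limited to eligible patients, and one exclusion criterion is timed at an infusion that only the VST arm receives, so one-sided removal after randomization is possible

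*Protocol*

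**What the plan says.** Protocol section 4.6 defines the population for every efficacy comparison: "All efficacy analysis will be based on the intent to treat (ITT) population, defined as eligible and randomized subjects".

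Section 2.6 uses a single list of criteria: "The same inclusion/exclusion criteria will apply to both phases of the study". Two items on that list refer to infusion:

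- Exclusion 2 in section 2.6.2: "Requiring mechanical ventilation at time of T cell infusion".
- Inclusion 1 in section 2.6.1, where the COVID test must fall no more than 5 "days prior to infusion".

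Section 2.6.3 sets the interval for the randomized phase: "once randomized to the treatment arm, the patient must be infused with VSTs within 48 hours of randomization". Section 2.7 gives the control arm neither infusion nor placebo. The primary response in section 2.2.1 is assessed by day 7 counted from randomization.

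On when eligibility is settled, section 2.6.3 says: "The informed consent process will begin at recognition of a subject who meets all eligibility criteria". Section 4.3 likewise describes the patients to be randomized as consented and eligible. Section 4.5 counts a death before day 7 as no response. No rule is given for a patient who is randomized to VST but never infused.

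**The concern.** The word eligible in section 4.6 acts as a filter on the randomized patients. A filter of that kind does little harm if every criterion is fixed before allocation and judged in the same way in both arms. Exclusion 2, as worded, meets neither condition in the randomized phase. It refers to a moment after allocation that exists in one arm only.

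Consider two patients intubated 24 hours after randomization. If the VST patient has not yet been infused, that patient meets an exclusion criterion and can be treated as outside the efficacy set. The control patient has no infusion time, cannot fail the criterion, and stays in. Both are very likely non-responders at day 7, and the window lies inside the primary endpoint period because the clock starts at randomization. Any removal through this route would therefore favour VST, in an open-label comparison with 20 patients per arm.

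The test-date criterion also works in one arm only. It is failed through delay and not through deterioration, so there is no reason to assume that patients removed by it are non-responders.

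**Working it through.** **Inputs.** From section 4.5: 20 patients per arm, expected response 90% (VST) and 50% (control), Fisher's exact test at a one-sided 5% level, stated power 83%. The share of VST patients ventilated between randomization and infusion is not given, so 0, 5, 10 and 15% are assumed for illustration. On 20 patients these are 0, 1, 2 and 3 expected removals.

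**Step 1: the plan's own figure.** Power = sum over all (a, b) with one-sided Fisher p ≤ 0.05 of Bin(a; 20, 0.9) × Bin(b; 20, 0.5), where a and b are the numbers of responders on VST and control. The result is 83.7%, so the stated 83% is confirmed and is not in question.

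**Step 2: effect of removal on a single result.** The one-sided Fisher p-value for a/n1 vs b/20, with m = a + b responders in total, is

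p = Σ(x ≥ a) C(n1, x) · C(20, m − x) / C(n1 + 20, m).

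For 18/20 vs 13/20 (m = 31): (14,728,800 + 2,519,400 + 167,960) / 273,438,880 = 0.064.

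After one VST non-responder is dropped, 18/19 vs 13/20: (1,472,880 + 125,970) / 61,523,748 = 0.026.

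Other tables by the same formula:

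| All randomized | p | One VST non-responder removed | Two removed |
|---|---|---|---|
| 18/20 vs 13/20 | 0.064 | 0.026 | – |
| 17/20 vs 12/20 | 0.078 | 0.039 | – |
| 16/20 vs 11/20 | 0.088 | 0.051 | 0.024 |
| 15/20 vs 10/20 | 0.095 | 0.060 | 0.033 |
| 18/20 vs 10/20 (planned rates) | 0.007 | 0.002 | – |

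One removal crosses 5% in the first two tables, and two are needed in the next two. At the planned rates the result is significant either way.

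**Step 3: type I error.** Let both arms have true response p, and let a share q of VST patients be non-responders who are removed. The number removed is k ~ Bin(20, q). The remaining 20 − k VST patients respond with probability p/(1 − q), and controls follow Bin(20, p). Summing the probability of all outcomes with one-sided p ≤ 0.05 gives:

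| Assumed removal q | 0% | 5% | 10% | 15% |
|---|---|---|---|---|
| Type I error, p = 50% (planned control rate) | 2.1% | 3.5% | 5.2% | 7.5% |
| Apparent VST response, 0.50/(1 − q) | 50% | 52.6% | 55.6% | 58.8% |
| Type I error, p = 70% | 2.7% | 4.1% | 7.1% | 12.3% |

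At smaller assumed rates of 1% and 3%, the error is 2.4% and 2.9% at 50% response, and 2.9% and 3.4% at 70%. Fisher's test is conservative at this sample size (2.1% actual against 5% nominal at 50% response). The inflation therefore passes the nominal level only at about 10% removal when response is 50%.

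**Step 4: with all randomized patients kept.** The arms stay at 20 and 20, and a VST patient ventilated before infusion counts like a control with the same course. Under no effect, the type I error is the q = 0 column.

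**The case against.** The strongest reply is that the protocol never orders such a removal. Section 2.6.3 starts consent with a subject who already meets all criteria, and section 4.3 randomizes eligible patients. Section 4.5 equates the 40 eligible patients of this phase with the 40 randomized. The only removal described (no matching line) comes before randomization, and the off-study criteria in section 3.4.3 mention neither ventilation nor missed infusion. Table 1 puts infusion (dose finding) and randomization (randomized phase) in the same Day 0 row, and section 3.3 times the schedule from one or the other by phase. Exclusion 2 could thus be read as a Day 0 criterion, or as a check before cells are given. On that reading nobody leaves the set.

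This stands as a fair alternative reading, and it limits the strength of the point. It does not remove it. A status at the time of infusion cannot be known at consent, and nothing in the protocol fixes eligibility at randomization. If the benign reading is the intended one, the word eligible in section 4.6 adds nothing and can be deleted without loss.

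Two further replies also stand. Entry requires SpO2 of at least 92% on room air and the window is at most 48 hours, so intubation before infusion should be uncommon; 10 to 15% is an upper illustration. And the planned result would not change in conclusion.

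A reader might infer more: that the protocol requires the removal, that both infusion-timed criteria remove deteriorating patients, or that everyone removed is a certain non-responder. The text does not support any of these. Removal is permitted and not required, only ventilation tracks deterioration, and very likely non-responder is as far as that criterion takes one.

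**Conclusion.** The point holds in limited form. The set labelled ITT is narrower than all randomized patients. Through exclusion 2 it can lose poor-prognosis patients after allocation from the VST arm only. At the planned 50% control rate and no effect, the type I error rises from 2.1% to 3.5%, 5.2% and 7.5% at assumed removal of 5, 10 and 15%. It stays under the nominal 5% at the lower rates, which are the more plausible ones. A single removal can reverse a borderline result, but not the planned one.

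These figures assume that all removed patients are non-responders and that the section 4.5 test (one-sided 5% Fisher) is used for the primary comparison. The removal rates are assumptions throughout. Severity is moderate: worth correcting before outcomes are known, because in an open-label trial the choice could not be made credibly afterwards, but not a defect that should hold up the trial.

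**What to change.** In section 4.6, define the ITT population as all randomized patients, analysed in the arm to which they were randomized whether or not they were infused. State that, for the efficacy set, eligibility is fixed at randomization, so that events between randomization and infusion never change membership.

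Reconcile the infusion-timed wording in sections 2.6.1 and 2.6.2 with the randomized phase, so that it is clear which criteria determine entry to the analysis and which are only checks before treatment is given. This concerns analysis membership and does not alter who may be infused.

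The cost is a few lines of wording. Sample size and the stated power calculation are unchanged. The downside is that a VST patient who cannot be infused remains as a probable non-responder and slightly dilutes the estimated effect.
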